7.3 Treatment Interruption

During the IV infusion all subjects should be monitored closely. Symptoms and signs that may occur as part of an infusion reaction include, but are not limited to: fever, chills, nausea, headache, bronchospasm, hypotension, angioedema, throat irritation, rash, pruritus, myalgia, and dizziness. In the event that a significant infusion reaction occurs, if the investigator determines necessary, supportive care should be employed in accordance with the symptoms/signs.

If the infusion is interrupted: the start and end time for each interruption, reason for interruption, if the administration was temporarily suspended and resumed, and if the full dose was administered, will be documented in the subject's source documents and eCRF.

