7.4 Individual Subject Discontinuation

7.4.1 Treatment Discontinuation

After treatment assignment, a subject may stop treatment permanently for a variety of reasons. Treatment discontinuations may be initiated by a subject who is not satisfied with treatment or may become medically necessary due to AE, required treatment with a disallowed medication or therapy, or other issues, as determined by the investigator.

If a subject is withdrawn from trial, the sponsor will be notified and the date and reason(s) for the withdrawal will be documented in the subject's eCRF. If a subject is withdrawn, efforts will be made to perform all discharge assessments, if possible ([Table 1.3-1](#)). Other procedures may be performed at the investigator's (or designee's) and/or sponsor's discretion. If the subject is in-house, these procedures should be performed before the subject is discharged from the clinic. The investigator (or designee) may also request that the subject return for an additional Follow-up visit. All withdrawn subjects will be followed until resolution of all their AEs or until the unresolved AEs are judged by the investigator (or designee) to have stabilized.

Subjects who do not complete the IV infusion of (¹⁴C)-OPC-61815 may be replaced, with up to a maximum of 10 subjects being dosed in total.

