8.8 Adverse Events

8.8.1 Definitions

An AE is defined as any untoward medical occurrence in a clinical trial subject administered an IMP and which does not necessarily have a causal relationship with this treatment. Adverse events would not include information recorded as medical history at Screening for pre-planned procedures for which the underlying condition was known and no worsening occurred. An adverse reaction is any untoward and unintended response to an IMP related to any dose administered.

A suspected adverse reaction is any AE for which there is a reasonable possibility that the IMP caused the AE.

Treatment-emergent AEs are defined as AEs with an onset date on or after the start of open-label treatment. In more detail, TEAEs are all AEs which started after start of open-label IMP treatment; or if the event was continuous from pre-IMP treatment and was worsening, serious, IMP-related, or resulted in death, discontinuation, interruption, or reduction of IMP.

An SAE includes any event that results in any of the following outcomes:

- Death.
- Life-threatening; ie, the subject was, in the opinion of the investigator, at immediate risk of death from the event as it occurred. It does not include an event that, had it occurred in a more severe form, might have caused death.
- Persistent or significant incapacity/disability or substantial disruption of the ability to conduct normal life functions.
- Requires inpatient hospitalization or prolongs hospitalization.
 - Hospitalization itself should not be reported as an SAE; whenever possible the reason for the hospitalization should be reported.
 - Hospitalizations or prolonged hospitalizations for social admissions (ie, those required for reasons of convenience or other nonmedical need) are not considered SAEs.
 - Prescheduled hospitalization to address a condition that has existed prior to the signing of the ICF should not be considered an SAE.

- Congenital anomaly/birth defect.
- Other medically significant events that, based upon appropriate medical judgment, may jeopardize the subject and may require medical or surgical intervention to prevent one of the outcomes listed above; eg, allergic bronchospasm requiring intensive treatment in an emergency room or home, blood dyscrasias or convulsions that do not result in hospitalization, or the development of drug dependency or drug abuse.

Nonserious AEs are all AEs that do not meet the criteria for a "serious" AE.

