Adverse Events of Special Interest: A noteworthy event for the particular product/IMP or class of products that a sponsor may wish to monitor carefully. All AESIs are to be reported as immediately reportable events (IREs).

Immediately Reportable Event:

- Any SAE.
- Any AE related to occupational exposure.
- Potential serious hepatotoxicity (see [Section 8.8.6](#)).
- Pregnancy in a female partner of a male subject are also defined as IREs. Although this will only occur in a female partner of a male subject, it must be reported on an IRE form and the Pregnancy Surveillance Form(s) to the sponsor. Pregnancy will only be documented on the AE eCRF if there is an abnormality or complication. This includes pregnancy of the partner of the subject.

Clinical Laboratory Test Value Changes: It is the investigator's responsibility to review the results of laboratory tests for each individual subject as they become available. This review will be documented by the investigator's dated signature on the laboratory report. The investigator may repeat the laboratory test or request additional tests to verify the results of the original laboratory tests. If this laboratory value is considered medically relevant (ie, clinically significant) by the investigator (subject is symptomatic, requiring corrective treatment or further evaluation), or if the laboratory value leads to discontinuation, and/or fulfills a seriousness criterion, this is considered an AE.

Severity: Adverse events will be graded on a 3-point scale and reported as indicated on the eCRF. The severity of an adverse experience is defined as follows:

1 = Mild: Discomfort noticed, but no disruption to daily activity.

2 = Moderate: Discomfort sufficient to reduce or affect normal daily activity.

3 = Severe: Inability to work or perform normal daily activity.

IMP Causality: Assessment of causal relationship of an AE to the use of the IMP is defined as follows:

Related: There is a reasonable possibility of a temporal and causal relationship between the IMP and the AE.

Not Related: There is no temporal or causal relationship between the IMP and the AE.

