8.8.2 Eliciting and Reporting Adverse Events

The investigator will regularly assess subjects for the occurrence of AEs. To avoid bias in eliciting AEs, subjects should be asked the nonleading question: “How have you felt since your last visit?” Subjects will also be encouraged to spontaneously report AEs occurring at any other time during the trial to the investigator (or designee).

All AEs (serious and nonserious) reported by the subject must be recorded on the source documents and eCRF provided by the sponsor. Adverse event collection will begin after a subject signs the ICF to Final Discharge from the trial.

Medical terminology should be used for AE reporting. Adverse events should be reported as a single unifying diagnosis whenever possible or, in the absence of a unifying diagnosis, as individual signs or symptoms.

In addition, the sponsor must be notified immediately by telephone, fax, or e-mail of any IREs according to the procedure outlined below in [Section 8.8.3](#). Special attention should be paid to recording hospitalization and concomitant medications.

Adverse event, start date, end date (if possible, start date and time, end date and time), seriousness, severity, relationship to trial treatment (IMP Causality), action taken with trial treatment and outcome will be recorded on the source documents and in the eCRF.

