9.4.2 Safety Analysis

9.4.2.1 Adverse Events

All AEs will be coded by system organ class and Medical Dictionary for Regulatory Activities (latest version at time of data reporting) preferred term. The incidence of the following events will be summarized:

- TEAEs
- TEAEs by severity
- TEAEs potentially causally related to the IMP
- TEAEs with an outcome of death
- Serious TEAEs
- TEAEs leading to withdrawal of IMP/withdrawal from study

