8.2. Subject Disposition and Population Assignment

Subject disposition and population assignment will be listed.

A summary table will be provided, based on the all subjects population.

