8.6. Safety and Tolerability Assessments

8.6.1. Adverse Events

All AEs will be coded using the Medical Dictionary for Regulatory Activities (MedDRA) Version 22.1 (or higher if upversioned during the study).

A treatment-emergent adverse event (TEAE) will be defined as an AE that starts during or after the start of the infusion, or starts prior to the start of the infusion and increases in severity after the start of the infusion.

A treatment-related TEAE will be defined as a TEAE with a relationship of related to the study treatment, as determined by the investigator.

All AEs will be listed. In addition to the data recorded in the database, the listings will include derived onset time and duration. Onset time will be calculated from the time of the start of the infusion for TEAEs only.

The frequency of subjects with TEAEs and the number of TEAEs will be summarized for the following categories:

- TEAEs (overall, serious, leading to discontinuation of study treatment, and leading to death)
- TEAEs by severity
- Treatment-related TEAEs (overall, serious, leading to discontinuation of study treatment, and leading to death)
- Treatment-related TEAEs by severity

The frequency of subjects will be summarized separately for TEAEs and treatment-related TEAEs by the following:

- System organ class, and preferred term (PT)
- PT

For the AE data the following rules will apply:

- For the derivation of TEAE status: If the start date/time of an AE is incomplete or missing, a AE will be assumed to be a TEAE, unless the incomplete start date/time or the end date/time indicates a AE started prior to the start of the infusion.
- For the derivation of treatment-related TEAE status: If the study treatment relationship for a TEAE is missing, a TEAE will be assumed to be a treatment-related TEAE.
- For the derivation of onset time: If the start date/time of an AE is missing, onset time will not be calculated. If the start date/time of an AE is incomplete, where possible, the minimum possible onset time will be calculated and presented in ‘ \geq DD:HH:MM’ format (eg, if the date/time of the start of the infusion is 01MAY2019/08:00 and recorded start date/time of an AE is 03MAY2019, then the minimum possible onset time will be calculated by assuming the AE started at the first hour and minute of 03MAY2019 [03MAY2019/00:00], thus will be presented as onset time \geq 01:16:00 in the listing).

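### SAP 8.6.1 narrows the protocol's TEAE definition and drops its study-withdrawal summary without declaring either, and its event count conflicts with its own counting rule

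*SAP*

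**What the plan says.** **Definition.** Protocol 8.8.1 defines TEAEs in two consecutive sentences. The first covers onset on or after the start of treatment. The second, offered as the detailed version, adds an event already under way before dosing "if the event was continuous from pre-IMP treatment and was worsening, serious, IMP-related, or resulted in death, discontinuation, interruption, or reduction of IMP". SAP 8.6.1 also takes every event starting from the beginning of the infusion, but accepts an earlier event only if it "starts prior to the start of the infusion and increases in severity after the start of the infusion".

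**Summaries.** Protocol 9.4.2.1 lists, among the incidences to be summarised, "TEAEs leading to withdrawal of IMP/withdrawal from study". SAP 8.6.1 lists TEAEs overall, serious TEAEs, those that stop study treatment and those that lead to death, and repeats these for treatment-related TEAEs. It has no category for leaving the study.

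**Counting.** SAP 8.6.1 undertakes to report both the number of subjects with TEAEs and the number of events. A later rule in the same section, worded for summary statistics in general, treats several TEAEs of one preferred term in a subject as a single TEAE at the highest severity.

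**Declaration.** SAP Section 1 states that the SAP overrides the protocol's statistical considerations and that substantial differences will be identified. Section 10 reports no significant changes.

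**The concern.** Safety and tolerability is the trial's only secondary objective, and the TEAE tables are its main summary. Because the SAP takes precedence, programmers will follow its narrower rule.

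Severity does not stand in for the dropped routes. Protocol 8.8.1 says of it: "Adverse events will be graded on a 3-point scale and reported as indicated on the eCRF". Those grades measure effect on daily activity. Seriousness has separate criteria, and action on the infusion is recorded in a separate field. A pre-dose event could therefore become serious, or halt the infusion, with no change of grade. It would then be missing from the TEAE tables, including the SAP's own rows for serious events and for events that stop treatment.

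A reader of the study report would also lack one summary that the protocol promises. Where events recur, the reader could see an event count that is really a count of subject-by-term pairs. Section 10 would tell that reader that nothing significant had changed.

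**Working it through.** The plan gives no figure of its own to reproduce here. The check is a comparison of texts with simple counts.

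**1. Routes to TEAE status for an event continuing from before dosing**

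| Route in protocol 8.8.1 | Kept in SAP 8.6.1? | Can arise in this design without worsening? |
|---|---|---|
| Worsening | Yes, as a rise in severity | n/a |
| Serious | No | Yes |
| IMP-related | No | Hardly: onset precedes the only dose |
| Death | No | Yes |
| Discontinuation of IMP | No | Yes |
| Interruption of IMP | No | Yes |
| Reduction of IMP | No | No dose reduction is planned |

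Dropped: 7 − 1 = 6. Still possible here: 6 − 2 = 4.

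The situation can occur. Adverse-event collection starts at consent (protocol 8.8.2), and screening runs within 28 days before dosing. Protocol 7.3 foresees interruption and requires a record of "if the administration was temporarily suspended and resumed". The SAP's default for missing start dates deals with incomplete dates only and restores none of the six routes.

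**2. Withdrawal summary**

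With one infusion of 55 to 65 minutes, study treatment can be discontinued only within that period. Subjects then stay until at least Day 9 and may be followed to Day 12. Protocol 7.4.2 names an adverse event as a reason for leaving the trial. A subject who completes the infusion and later leaves because of an adverse event falls outside the SAP's treatment-discontinuation row. Categories for study withdrawal: 1 in the protocol, 0 in the SAP.

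SAP 8.2 says of disposition: "A summary table will be provided, based on the all subjects population". It does not say whether reasons for withdrawal will appear.

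**3. Event count against the collapsing rule**

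A subject with *k* events of one preferred term contributes *k* to an event count but 1 under the rule, a loss of *k* − 1. Protocol 2.4.1 gives two illustrations.

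- Single-dose trial 263-08-001: three terms with 2 occurrences each, each in at least 2 subjects. Events: 3 × 2 = 6. Subject-by-term pairs: 3 × 2 = 6. Loss: 1 − 6/6 = 0%. The other 24 − 6 = 18 events are not itemised.
- Multiple-dose trial 263-09-001, terms seen in at least 3 subjects. Events: 39 + 31 + 5 + 4 + 24 + 8 + 4 = 115. Pairs: 9 + 5 + 5 + 4 + 3 + 3 + 3 = 32. For feeling abnormal alone, 39 events become 9.

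The second trial gave repeated daily doses by rapid injection, so it shows how far the two counts can part and does not predict this trial. The first is closer in having a single dose.

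**4. Effect of one omitted subject on a row**

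1/10 = 10.0% and 1/8 = 12.5%, so a row's incidence moves by 10.0 to 12.5 percentage points.

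**The case against.** **On the definition.** The protocol's first sentence covers onset only, so the SAP sits between the two: wider than the first and narrower than the second. Death and most serious outcomes would usually bring a rise in grade. An event already severe at dosing is unlikely, because subjects must have no clinically significant findings at Screening and Check-in. The realistic remainder is a mild or moderate event that interrupts or stops the infusion at unchanged grade. Neither document has an interruption row, and interruptions go on the eCRF anyway. All this limits how often the gap will matter. It does not reconcile the texts, since the SAP matches neither protocol sentence.

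**On withdrawal.** The protocol joins the two ideas with a slash and blurs them in 7.4.1 and 7.4.2, so the SAP row might be shorthand for both. For each event, protocol 8.8.2 says that "action taken with trial treatment and outcome will be recorded" and names no field for study withdrawal. The SAP's wording nevertheless refers to treatment alone. Subjects who discontinue will be identified in the listings, so the information survives there but not in a TEAE summary.

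**On counting.** The rule may be a deliberate convention meant for the by-term and by-severity tables. This is the softest of the three points. As written, though, it makes no exception for the event count.

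**On declaration.** Only substantial differences have to be identified, and no threshold is given. The sponsor could call these minor. Still, changing which events qualify as TEAEs and omitting a named summary belong in Section 10.

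**Conclusion.** The point holds. The narrower TEAE definition and the missing study-withdrawal summary are undeclared departures from the protocol. The counting conflict is an inconsistency within the SAP, not a departure from the protocol, and rests on weaker ground.

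The practical size is modest. At most 10 subjects are dosed, the safety analysis is descriptive, no primary endpoint is touched and all adverse events are listed. The shift of 10.0 to 12.5 points is conditional on one subject being affected; the documents give no basis for estimating how likely that is. The effect of the counting rule is expected to be small and could be zero.

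The conclusion assumes that the SAP is followed as written. The table shells, which were not available, could resolve the withdrawal row or the counting rule. The SAP should be corrected before database lock.

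**What to change.** In SAP 8.6.1:

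1. Use the second, detailed sentence of protocol 8.8.1 as the TEAE definition, because the sentence before it covers onset after treatment start only. Otherwise, declare the narrower rule in Section 10.
2. Add a row for TEAEs leading to study withdrawal, or declare its omission in Section 10. The source is the eCRF, where under protocol 7.4.1 "the date and reason(s) for the withdrawal will be documented in" the subject's record; 7.4.2 supplies the list of reasons.
3. Limit the collapsing rule to subject counts by preferred term and maximum severity, so that the number of TEAEs counts every event.

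The cost is SAP wording and one extra table row, with no new data collection. Because no adverse-event field for study withdrawal is named, item 2 needs each withdrawal attributed to an adverse event to be matched to the corresponding event record. With no more than 10 subjects, that is a small task.

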8.6.2. Clinical Laboratory Parameters

All clinical laboratory parameters will be listed; any value outside the clinical reference range will be flagged. Separate listings will be provided for any parameter for which there is any individual subject value outside the respective clinical reference range.

Summary tables and boxplots by timepoint will be provided for serum chemistry and hematology parameters.

Values recorded as $< x$, $\leq x$, $> x$, or $\geq x$ will be displayed in the listings as recorded. For the derivation of listing flags, calculation of summary statistics, and presentation in the figures, $< x$ and $\leq x$ values will be set to 0, whereas $> x$ and $\geq x$ values will be set to x .

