5. SAMPLE SIZE JUSTIFICATION

No formal statistical assessment of sample size has been conducted. The sample size chosen for this trial is common in human radiolabeled studies and is considered sufficient to achieve the objectives of the trial. It is planned for at least 8 healthy male Japanese subjects to be dosed to ensure that 6 subjects complete the IV infusion. Up to a maximum of 10 subjects will be dosed in total.

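### Laboratory out-of-range flags are derived from substituted numbers (0 for `<x`, x for `>x`), so some combinations of reporting limit and reference range can misflag a result

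*SAP*

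**What the plan says.** SAP 8.6.2 lists all laboratory parameters and promises that "any value outside the clinical reference range will be flagged". It adds: "Separate listings will be provided for any parameter for which there is any individual subject value outside the respective clinical reference range". It also states: "Summary tables and boxplots by timepoint will be provided for serum chemistry and hematology parameters". Urinalysis, which is in the test panel of Protocol Appendix 2, is therefore listed and flagged but not summarized.

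Results reported with an inequality sign "will be displayed in the listings as recorded". A numeric substitution applies to everything else, with this scope: "For the derivation of listing flags, calculation of summary statistics, and presentation in the figures". Under it, `<x` and `≤x` "values will be set to 0, whereas" `>x` and `≥x` "values will be set to x".

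Neither document gives reporting limits or reference ranges, or says which analytes are expected to produce such results.

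**The concern.** A flag needs no substituted number. The recorded inequality often settles whether a result is out of range, and where it does not, the honest answer is that the status is unknown. The SAP replaces the inequality with a number and compares that number with the range, so information already in the record is lost. This can break the section's own undertaking to flag every out-of-range value. It can also affect the separate listings, because a parameter earns one only if some value is judged out of range.

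For elevations the choice is the least cautious available, since `>x` becomes the smallest value the record allows. For adverse events, by contrast, SAP 8.1.1 and 8.6.1 take a worst-case approach to missing information. Laboratory evaluations are a named secondary endpoint (SAP section 3). With so few subjects, a single substituted value can visibly move a mean or a boxplot.

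**Working it through.** **Inputs.** The substitution rule, its scope and the flag definition are in SAP 8.6.2. The number of subjects is from SAP section 5: "It is planned for at least 8 healthy male Japanese subjects to be dosed to ensure that 6 subjects complete the IV infusion", with a maximum of 10. I use n = 6, 8 and 10. The plan states no figure for this point, so there is none to reproduce. LLN and ULN are the lower and upper limits of the reference range. I assume that values cannot be negative and that an upper reporting limit is not below LLN.

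**Flags.** For each position of x, compare the flag the rule gives with what the record allows.

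| Recorded | Position of x | Number used | Flag under the rule | What the record allows | Outcome |
|---|---|---|---|---|---|
| `<x` | LLN = 0, x ≤ ULN | 0 | none | normal | correct |
| `<x` | 0 < x ≤ LLN | 0 | low | low | correct |
| `<x` | 0 < LLN < x ≤ ULN | 0 | low | low or normal | may be false |
| `<x` | LLN > 0, x > ULN | 0 | low | low, normal or high | may be false |
| `≤x` | x < LLN | 0 | low | low | correct |
| `≤x` | x = LLN > 0 | 0 | low | low, or exactly LLN | false only if the value equals LLN |
| `>x` | x < ULN | x | none | normal or high | a high may be missed |
| `>x` | x = ULN | x | none | high | a high is certainly missed |
| `>x` | x > ULN | x | high | high | correct |
| `≥x` | x ≤ ULN | x | none | normal or high | a high may be missed |
| `≥x` | x > ULN | x | high | high | correct |

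For x above a positive LLN, `≤x` behaves as `<x` does.

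Two instances with an assumed range of 1 to 10:
- `<2` becomes 0 and is flagged low, although a true 1.5 would be normal.
- `>10` becomes 10 and is not flagged, although every value above 10 is out of range.

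**Means.** Each substitute is the lowest value the record allows, so the mean is never shifted upward. If k of n values are `<x`, each true value lies between 0 and x, and the shift lies between 0 and −kx/n.

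- k = 1: at most 1/6 = 0.167x (n = 6), 1/8 = 0.125x (n = 8), 1/10 = 0.100x (n = 10).
- Half the values censored: at most 0.5x at any n.
- Measured against x/2 instead of the lowest possible mean, these figures halve.
- For `>x` the rule itself sets no limit on the downward shift.

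**Illustration with assumed data.** n = 8, three values `<3`, the others 4, 5, 6, 8 and 10 (sum 33).

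| `<3` set to | Mean | SD | Minimum | Median |
|---|---|---|---|---|
| 0 | 33/8 = 4.125 | 3.871 | 0 | 4.5 |
| x/2 = 1.5 | 37.5/8 = 4.688 | 3.206 | 1.5 | 4.5 |
| x = 3 | 42/8 = 5.250 | 2.605 | 3 | 4.5 |

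The mean, SD and minimum depend on the convention. The median does not here, because fewer than half the values are censored.

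**The case against.** The strongest reply is that nothing shows the problem will arise. No analyte is known to have a reporting limit in the troublesome position. If x is at or below LLN for `<x`, or the upper reporting limit lies above ULN, the flags are right. They are also right for `<x` when LLN is 0 and x does not exceed ULN. This stands, and it is why the point must be put conditionally.

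It also stands that safety oversight does not run through these flags. The recorded string stays in the listings. The investigator assesses all laboratory data (Protocol 8.7.1) and reviews and signs each laboratory report, and a value judged clinically significant is an adverse event (Protocol 8.8.1). The hepatotoxicity rule in Protocol 8.8.6 works on the values themselves. A reader might infer that a safety signal could be lost, but the documents do not support that. A missed flag is a display omission. It removes a parameter's separate listing only if no other value of that parameter is out of range.

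Substituting x or x/2 in the summaries would be another convention, not a correction. Setting `<x` to x can shift the mean upward by as much as 0 can shift it downward, kx/n. Nor are the two directions inconsistent, since both take the lower bound.

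None of this defends the rule for flags, where no substitution is needed and one configuration gives a certain error.

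**Conclusion.** The point holds in conditional form. The rule can produce a false low flag when 0 < LLN < x, or for `≤x` when x = LLN > 0. It certainly misses a high for `>x` when x = ULN. It may miss one for `>x` when x < ULN and for `≥x` when x ≤ ULN. If censored values occur in serum chemistry or hematology, means can only move downward, by up to kx/n for `<x`, and the minimum, SD and boxplots are distorted.

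It would be tempting to say that the rule does create false flags, hide highs and bias means in this trial. The documents do not support this, because they give neither limits nor ranges and the number of affected analytes is unknown. Nor would a displayed mean be near 0 whatever the truth. That would need almost every value to be censored, and the true values would then lie below x in any case. A move from `<x` to x would not read as a rise from 0 to x in the listings, which show the string, and SAP 8.6.2 plans no change-from-baseline summary.

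The consequence is limited to descriptive secondary safety output. The primary PK endpoints do not use this rule (SAP 8.5 has its own rules for values below quantification), and no inferential analysis is planned.

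**What to change.** In SAP 8.6.2, take the flags out of the substitution rule and derive them from the recorded value with its sign:

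- `>x`: high if x ≥ ULN.
- `≥x`: high if x > ULN.
- `<x`: low if x ≤ LLN.
- `≤x`: low if x < LLN.
- Any other censored result that could be out of range: mark as indeterminate.

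For summaries and figures, one stated convention may stay. Footnote the substitution used and the number of censored values per parameter and timepoint.

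The cost is one SAP sentence and minor programming, with no extra data collection.
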